13.3.3 Potential Drug-induced Liver Injury (DILI)

Signals of DILI will be assessed according to the FDA guideline⁶ using the following criteria:

- ALT or AST $>2\times$, $>3\times$, $>5\times$, $>10\times$, or $>20\times$ ULN
- total bilirubin (BILI) >2×ULN
- alkaline phosphatase (ALP) >1.5×ULN
- ALT or AST >3×ULN AND total bilirubin >1.5× or >2×ULN

Patients fulfilling any of the criteria in the Placebo-controlled Period will be listed for inclusion in the *CSR*, and the listing will include all the ALT, AST, BILI, and ALP values for those patients prior to entering the Extension Period, sorted by assessment date and time in ascending order. If a criterion for a test is fulfilled, the value will be flagged with the highest criterion fulfilled (for example, AST >3×ULN, >5×ULN, >10×ULN, or >20×ULN).

A similar listing will be provided including all the ALT, AST, BILI and ALP values for the patients fulfilling any of the criteria in the Extension Period for inclusion in the *addendum to CSR*.

In addition, assessment time points for patients for whom Hy's Law is potentially fulfilled will also be flagged in the listings (pHYL):

- ALT or AST $>3\times$ ULN AND
- alkaline phosphatase <2×ULN AND
- total bilirubin $\geq 2 \times ULN$

The number of patients who met any of the criteria specified above at any post-baseline visit will be summarized by treatment group and period. In the summaries, each patient will be counted only once using the maximum assessment, or the most severe for the combined criteria. The summaries will also include the number of potential Hy's Law cases.

13.4 Vital Signs and Weight

The PCS criteria used for vital signs and weight are the Lundbeck standard PCS criteria described in SOP_09978: *GPV – PCS and standard reference values for laboratory investigations, vital signs and ECGs in clinical studies*, version 6, and are also included in Table 4.

13.5 ECGs

The PCS criteria used for the ECG parameters are the Lundbeck standard PCS criteria described in SOP_09978: *GPV – PCS and standard reference values for laboratory investigations, vital signs and ECGs in clinical studies*, version 6, and are also included in Table 5.

In addition to the tables and listings specified in Section 13.2, absolute values and changes from Baseline in QTcF will also be summarized categorically by visit and treatment, separately for the Placebo-controlled Period and the Extension Period. The categories that will be used are as follows for the absolute QTcF values:

- QTcF interval < 450 msec
- QTcF interval 450 480 msec
- QTcF interval > 480 500 msec
- QTcF interval > 500 msec

The categories that will be used for the change from baseline QTcF values are:

- QTcF interval increase from baseline > 30 msec
- QTcF interval increase from baseline > 60 msec

Furthermore, the number and percentage of patients being classified as having either a normal, abnormal but not clinically significant, abnormal and clinically significant ECG result

based on the overall interpretation of the ECG from the investigator will be summarized by visit and treatment group, separately for each period.

13.6 Other Safety Endpoints

13.6.1 Columbia-Suicide Severity Rating Scale (C-SSRS) Scores

The C-SSRS was administered:

- for lifetime (using the *Baseline/Screening Version*) the C-SSRS assessment at screening that collects a lifetime recall
- for the past 12 months at screening (using the *Baseline/Screening Version*) the C-SSRS assessment at screening that focuses on the last 12 months
- at baseline (using the *Since Last Visit Version*) the C-SSRS assessment at baseline that collects information since the previous visit
- post-baseline (using the Since Last Visit Version) the C-SSRS assessments after baseline

The numbers and percentages of patients with lifetime, past 12 months, baseline, or postbaseline suicide-related events based on the C-SSRS will be summarized by treatment group. For each summary, the most severe item with an answer "Yes" for each patient according to the ordering given in Panel 4 is displayed. For the post-baseline assessments, the summaries will be by treatment group and period and the most severe item with an answer "Yes" for the whole period for each patient related to suicidal ideation and/or behaviour will be summarized.

The number and percentage of patients with *no suicidal ideation or behaviour* will be included in the summaries.

C-SSRS Score		Related to:	
1	Wish to be dead	Suicidal ideation	
2	Non-specific active suicidal thoughts		
3	Active suicidal ideation with any methods (not plan) without intent to act		
4	Active suicidal ideation with some intent to act, without specific plan		
5	Active suicidal ideation with specific plan and intent		
6	Preparatory acts or behaviour	Suicidal behaviour	
7	Aborted attempt		
8	Interrupted attempt		
9	Non-fatal suicide attempt		
10	Completed suicide (only applicable for the post-baseline assessments)		

Panel 4	C-SSRS Scores
	C-BBIG BUILS

The C-SSRS scores will be summarized based on the APTS for the lifetime, past 12 months, baseline and Placebo-controlled Period summaries and based on the APTS_LT for the

Extension Period summary. Patients with at least one C-SSRS assessment in the period will be included, regardless of whether they had a baseline C-SSRS assessment.

Missing C-SSRS scores will not be imputed.

Positive responses to non-suicidal self-injurious behaviour will be summarized separately.

For patients with any post-baseline suicidal ideation or behaviour in the Placebo-controlled Period (C-SSRS scores of 1 to 10), listings will be provided based on APRS including all C-SSRS scores prior to entering the Extension Period for those patients for inclusion in the *CSR*.

A similar listing will be provided for patients with any post-baseline suicidal ideation or behaviour in the Extension Period including all the C-SSRS scores for those patients for inclusion in the *addendum to CSR*.

14 Blinded Data Reviews

The quality of the study will be overseen by performing blinded data reviews during the conduct of the study. The reviews may include, but are not limited to, data quality, protocol adherence, and the appropriateness of design assumptions, including the sample size assumptions.

An independent Safety Data Monitoring Committee (DMC) will regularly monitor the patients' safety data according to the *DMC Charter*. The DMC will have access to unblinded information for the double-blind treatment for each patient. Members of the DMC will not be involved in other study-related tasks.

15 Interim Analyses

See Section 18.

16 Sample Size Considerations

The two prior eptinezumab Phase III studies, PROMISE-1 performed in an EM population and PROMISE-2 performed in a CM population, had the following effect sizes for the primary endpoint when compared to placebo (standard deviations):

- EM: 100 mg 0.69 (3.1), 300 mg 1.11 (3.1)
- CM: 100 mg 2.03 (5.8), 300 mg 2.60 (5.8)

The power was determined by simulating the testing strategy (10000 simulations) assuming normal distributions with similar mean and SD for continuous endpoints and similar success rates as the response variables in the Phase III studies for the corresponding population (EM or CM) without assuming the variables to be correlated. With 280 patients per treatment group, assuming that 40% of the patients will be from the EM population and 60% from the

CM population, and that 2% of the patients not having a post-baseline assessment of the primary endpoint, simulations show that the power for the test of the primary endpoint is approximately 94% for the comparison of 100 mg to placebo and 99% power for the comparison of 300 mg to placebo. The individual key secondary endpoints had a power of at least 68% for showing an effect, with a combined power of 58% for seeing an effect for all primary and key secondary endpoints and both doses in the testing strategy.

17 Statistical Software

The statistical software used will be SAS[®], Version 9.4 or later.

18 Changes to Analyses Specified in the Protocol

In the *Clinical Study Protocol* (ed. 1.0 and 2.0), it is described that an unblinded interim analysis for efficacy will be performed, when 345 patients have been randomized and received the first infusion of IMP and have had the opportunity to complete the Primary Outcome Visit (Week 12). The analysis was intended to allow for stopping the study for efficacy if the results fulfilled the interim criteria. Based on the result of the interim analysis, Lundbeck could decide to stop the study for efficacy or continue the enrolment. Due to recruitment being faster than expected, it has been decided not to conduct the interim analysis after all. Therefore, any references to the interim analysis have been removed from the *Statistical Analysis Plan*, and the significance level to be used in the testing strategy has been updated to 0.05.

The wording of endpoints related to HCRU has been updated since it is not the changes from baseline but the frequency of responses in each category that will be summarized for the study.

The wording of endpoints related to MBS has been updated to reflect that the MBS score in itself reflects a change from baseline.

HIT-6 responder endpoints have been added to the list of secondary endpoints.

In relation to the addition of HIT-6 response endpoints, responder analyses using logistic regression have been added to the list of secondary analyses.

According to the original *Clinical Study Protocol* ed. 1.0, the primary analysis of the primary endpoint has been updated from an ANCOVA using the average values of MMDs over Weeks 1-12 to an MMRM using the available monthly values of MMDs. This update is included in an amendment of the *Clinical Study Protocol*, resulting in a *Clinical Study Protocol* ed. 2.0, dated 22 January 2021.

According to the original *Clinical Study Protocol* ed. 1.0, the key secondary analyses of key secondary responder endpoints (50% response (Weeks 1-12) and 75% response (Weeks 1-12)) have been updated to logistic regressions instead of the CMH tests specified in the

protocol. This update is included in an amendment of the *Clinical Study Protocol*, resulting in a *Clinical Study Protocol* ed. 2.0, dated 22 January 2021.

The definition of a *treatment-emergent adverse event* (TEAE) has been updated to clarify that the time of infusion is also taken into account in the classification.

For the numerical representation of PGIC scores, the score 1 is used to represent a score of "very much improved" and a score of 7 to represent a score of "very much worse". This is the opposite of what is described in the protocol, where it is stated that a high score indicates improvement.

19 Details on Data Handling

19.1 Derived Variables

19.1.1 eDiary

19.1.1.1 Monthly Migraine Days (MMDs)/Monthly Headache Days (MHDs)

The following describes the derivation of MMDs. The derivation of MHDs follows the same principles.

4-Week Intervals

For Baseline and each 4-week period post-baseline in the study, the number of MMDs will be derived as the number of migraine days within each 28-day interval using the imputation rules described below. The 4-week periods post-baseline that are considered are the following: Weeks 1-4, Weeks 5-8, Weeks 9-12, Weeks 13-16, Weeks 17-20, Weeks 21-24, Weeks 25-28, Weeks 29-32, Weeks 33-36, Weeks 37-40, Weeks 41-44, Weeks 45-48, Weeks 49-52, Weeks 53-56, Weeks 57-60, Weeks 61-64, Weeks 65-68, Weeks 69-72.

In general, for 4-week periods where the eDiary is completed on at least 14 days out of the 28 days, prorating will be used to calculate the MMDs, and for 4-week periods where the eDiary is completed on less than 14 days out of the 28 days, the MMDs will be set to missing. However, there are cases where weighting will be used when less than 14 days have been completed, and an overview is given in Panel 5.

Prorating

Intended to be used for 4-week periods where the eDiary is completed on at least 14 out of the 28 days, the prorating procedure consists of imputing days with missing information with the observed mean number of migraine days in the period as follows:

28*(Reported Migraine Days/Reported eDiary Days)

This imputation rule will also be used for the Baseline value regardless of the number of reported eDiary days in the screening period. Patients are, however, required to demonstrate compliance with the eDiary and fill it out for at least 24 out of the 28 days in the screening period in order to be eligible for randomization.

Weighting

Intended to be used in special cases for the first 4-week period post-baseline, where the eDiary is completed on less than 14 days out of the 28 days due to withdrawal. When weighting is used, the number of MMDs is derived as a weighted sum of the observed mean number of migraine days in the period and the mean MMDs for the preceding period as follows:

$$28*(W*X + (1 - W)*X_p),$$

where $W = Reported \ eDiary \ Days/13$, $X = Reported \ Migraine \ Days/Reported \ eDiary \ Days$, and $X_p = preceding \ MMDs/28$.

Patients who withdraw due to lack of efficacy so early that they only have post-baseline data from Weeks 1-4 will have their MMDs calculated using weighting for Weeks 1-4 if they have less than 14 days of eDiary reporting during the first 4 weeks of the study. If they have 14 days or more in this period, their MMDs for Weeks 1-4 will be calculated using prorating.

Patients who withdraw due to adverse events so early that they only have post-baseline data from Weeks 1-4 will have their MMDs calculated using weighting for Weeks 1-4 if they have less than 14 days of eDiary reporting during the first 4 weeks of the study. If they have 14 days or more in this period, their MMDs for Weeks 1-4 will be calculated using prorating.

	Number of Reported eDiary Days		ed eDiary Days in Period
Description	4-Week Period	0-13	14-28
All patients randomized	Baseline	Prorating*	Prorating
Patients not withdrawing due to lack of efficacy/adverse event	Weeks 1-4	None (missing)	Prorating
Patients not withdrawing due to lack of efficacy/adverse event	4-week periods after week 4	None (missing)	Prorating
Patients withdrawing due to lack of efficacy	Weeks 1-4	Weighting	Prorating
Patients withdrawing due to lack of efficacy	4-week periods after week 4	None (missing)	Prorating
Patients withdrawing due to adverse event	Weeks 1-4	Weighting	Prorating
Patients withdrawing due to adverse event	4-week periods after week 4	None (missing)	Prorating

Panel 5 Overview of Imputation Rules for 4-Week Periods for eDiary Data

*Patients are required to complete the eDiary for at least 24 days during the first 28 days of screening to be eligible

In case of a reporting day where a patient answers in the evening diary that they experienced a headache on that day but then never fills out an actual headache in the headache diary, the day will be assigned as a no headache and no migraine day.

When the number of MMDs have been calculated for a given 4-week period, the result will be rounded to two decimals.

19.1.1.2 Migraine/Headache Responder Rates

The following describes the derivation for monthly migraine days. The derivation for monthly headache days is similar.

The following responder rates will be derived: 50%, 75%, and 100%. A responder is a patient, who achieves a \geq 50% reduction, \geq 75% reduction, or 100% reduction in MMDs, respectively, compared to the baseline number of MMDs. The derivation of these responder endpoints will be based on the number of MMDs resulting from the imputations described in Section 19.1.1.1.

For each 4-week period post-baseline in the study, the responder status of a patient will be derived based on the percentage change from baseline in MMDs. If the MMDs value is missing for the month in question, the response status will also be missing.

For the 12-week and 24-week intervals, the 50% and 75% responder status will be derived as follows, using 50% response for Weeks 1-12 as an example:

50% Responder Status(Weeks 1 - 12) =
$$\begin{cases} 1, & \text{if } \frac{\operatorname{ave}(\Delta_{M1}, \Delta_{M2}, \Delta_{M3})}{Baseline} \leq -0.5\\ 0, & \text{if } \frac{\operatorname{ave}(\Delta_{M1}, \Delta_{M2}, \Delta_{M3})}{Baseline} > -0.5, \end{cases}$$

where Δ_{Mi} is the change from baseline value for month *i*. For 12-week intervals, if any of the months included in the calculation have a missing value of MMDs, the responder status will be derived based on the available values. For 24-week intervals, the responder status will only be calculated if at least one observation from each 12-week period is available, i.e. it will be non-missing if there is one observation from one of Weeks 1-4, Weeks 5-8, or Weeks 9-12 and one of Weeks 13-16, Weeks 17-20, or Weeks 21-24.

The 100% responder rate for the 12-week and 24-week intervals will be derived based on the average 100% responder status for the 4-week intervals included in the interval, i.e. if a patient has 100% response for Weeks 1-4 and Weeks 5-8 but not for Weeks 9-12, the 100% responder rate will be 0.67 (computed as (1 + 1 + 0)/3), since the responder status for the first and second month for the patient was 1 and the responder status for the third month was 0. If any of the months included have a missing value of MMDs, the patient will be imputed with a non-response, i.e. with the value 0, for the 12-week or 24-week interval.

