	 Secondary endpoints: Response: patients with 50% reduction from baseline in monthly migraine days (Weeks 13-24) Response: patients with 75% reduction from baseline in monthly migraine days (Weeks 13-24) Response: patients with 100% reduction from baseline in monthly migraine days (Weeks 1-12) Response: patients with 50% reduction from baseline in monthly headache days (Weeks 1-12) Response: patients with 75% reduction from baseline in monthly headache days (Weeks 1-12) Response: patients with 75% reduction from baseline in monthly headache days (Weeks 1-12) Response: patients with 100% reduction from baseline in monthly headache days (Weeks 1-12) Change from baseline in the number of monthly headache days (Weeks 1-12) Change from baseline in percentage of migraines/headaches with severe pain intensity (Weeks 1-12) Change from baseline in the number of monthly days with use of acute migraine medication (Weeks 13-24) Change from baseline in the number of monthly days with use of acute migraine medication (Weeks 13-24) Change from baseline in the number of monthly migraine days with use of acute medication (Weeks 13-24) Change from baseline in the number of monthly migraine days with use of acute medication (Weeks 13-24) Change from baseline in number of monthly migraine days with use of acute medication (Weeks 13-24) Change from baseline in number of monthly migraine days with use of acute medication (Weeks 13-24) Change from baseline in number of monthly migraine days with use of acute medication (Weeks 13-24) Change from baseline in number of monthly migraine days with use of acute medication (Weeks 13-24) Change from baseline in number of monthly migraine days with use of acute medication (Weeks 13-24) PGIC score at Week 24 Change from baseline in the number of monthly migraine days in patients with Medication Overuse Headac	

Panel 1 Objectives and Endpoints

Objectives	Endpoints
	 Exploratory endpoints: Change from baseline in the number of monthly headache episodes for each 12-week period Change from baseline in the number of monthly migraine attacks for each 12-week period
 Secondary Objectives To evaluate the health-related quality of life and work productivity impact of optimory make 	 Key secondary endpoints: Change from baseline to Week 12 in the Headache Impact Test (HIT-6) score

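### The 100% responder score in SAP 19.1.1.2 ranks a patient with a missing month below one who failed that month (0 against 0.67)

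*SAP*

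**What the plan says.** SAP section 19.1.1.2 first describes response at patient level: "A responder is a patient, who achieves a" reduction of the stated size in MMDs, with MHDs handled in the same way. For 100% response over 12 or 24 weeks it switches to a fractional score, which "will be derived based on the average 100% responder status for the 4-week intervals included in the interval". Its worked example is a patient with 100% response in Weeks 1-4 and 5-8 "but not for Weeks 9-12, the 100% responder rate will be 0.67".

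The missing-data sentence follows at once. "If any of the months included have a missing value of MMDs", then "the patient will be imputed with a non-response, i.e. with the value 0, for the 12-week or 24-week interval". The zero is attached to the interval and not to the month.

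For 50% and 75% response the same section defines a yes/no status. If a month is missing from a 12-week interval, "the responder status will be derived based on the available values".

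Under section 19.1.1.1 and Panel 5, a month is missing when the eDiary was completed on fewer than 14 of its 28 days. The exception is Weeks 1-4 for patients withdrawing for lack of efficacy or an adverse event, where a weighting rule supplies a value. After Week 4 there is no exception.

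Section 12.5 analyses the 100% endpoints with an extended CMH test and presents the rates. The code in Appendix IV outputs the row-mean-score statistic on the analysis value, so fractional scores enter the test as they stand. The missing-month sensitivity analysis in section 12.4.4 covers only 50% and 75% response.

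**The concern.** Setting a whole patient to non-response is a coherent conservative rule for a yes/no status, because 0 is the worst value that the patient could have earned. It is not coherent for a score that gives partial credit. A patient who has responded in two months has already earned at least 0.67, whatever the third month would have shown. Setting the interval to 0 goes below the worst possible outcome and discards months that were observed. The SAP gives no reason for combining partial credit with all-or-nothing handling of missing months.

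Two things are at stake. The reported rates fall as more patients have a gap. And if gaps are more frequent in one arm, that arm is penalised by more than the missing months themselves could justify, and the penalty reaches the p-value.

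**Working it through.** **Scores under the written rule.** Let s1, s2, s3 be the monthly statuses. The score is (s1+s2+s3)/3 if all are observed, and 0 if any is missing. The SAP's own figure reproduces: (1+1+0)/3 = 0.67.

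| Monthly pattern | SAP rule | Only the missing month set to 0 |
|---|---|---|
| 1, 1, 1 | 1.00 | 1.00 |
| 1, 1, 0 | 0.67 | 0.67 |
| 1, 1, missing | 0 | 0.67 |
| 1, 0, 0 | 0.33 | 0.33 |
| 1, 0, missing | 0 | 0.33 |
| 0, 0, missing | 0 | 0 |
| 24 weeks: five 1s, one 0 | 0.83 | 0.83 |
| 24 weeks: five 1s, one missing | 0 | 0.83 |

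The ranking is reversed whenever at least one observed month is a 100% response, and only then.

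**Effect on group rates.** The documents give no monthly 100% response rate and no rate of missing months, so the inputs here are assumptions. Let p be the monthly rate, m the share of months missing and g the share of patients with any gap, with missingness unrelated to response. Then

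- SAP rule: expected rate = p × (1 − g)
- month-level non-response: expected rate = p × (1 − m)

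If months go missing independently, g = 1 − (1 − m)³. The within-patient correlation of response does not enter either formula.

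*Equal missingness, p = 12% and 5%.*

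- m = 5%: g = 1 − 0.95³ = 14.3%. The SAP rule gives 10.3% / 4.3%, and month-level non-response gives 11.4% / 4.8%.
- m = 8%: g = 1 − 0.92³ = 22.1%. The SAP rule gives 9.3% / 3.9%, and month-level non-response gives 11.0% / 4.6%.
- The factor (1 − g) is common to both arms, so the ratio stays at 12/5 = 2.40. Only the absolute rates and their difference shrink.

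*Unequal missingness, p = 10% in both arms, m = 3% versus 8%.*

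- SAP rule: 10% × 0.97³ = 9.1% and 10% × 0.92³ = 7.8%, a spurious difference of 1.3 points.
- Month-level non-response: 10% × 0.97 = 9.7% and 10% × 0.92 = 9.2%, a difference of 0.5 points.

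*Clustered missingness.* The FAS requires at least one valid 4-week assessment in Weeks 1-12, so an FAS patient can miss at most two of the three months. If every gap is two months long, g = 3m/2. For m = 3% and 8% the SAP rule then gives 10% × 0.955 = 9.55% and 10% × 0.88 = 8.80%. That is a difference of 0.75 points, still against 0.5.

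**The label.** With nothing missing, the group mean equals p, the average fraction of responding months. It is the share of patients responding in every month only if no patient has a mixed pattern. With p = 10% and a beta-binomial model for the three months, that share is 1.9%, 5.0% or 8.7% at an assumed within-patient correlation of 0.3, 0.6 or 0.9.

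**The case against.** The strongest reply is that little turns on this. The reversal needs a missing month together with an observed 100%-response month. A month is lost only below 14 diary days, while Protocol section 9.2.2 asks for at least 85% compliance and section 8.1 has it checked every 4 weeks. Withdrawal clusters missing months in the same patients, which reduces the effect. Nothing in the documents supports 14% or 22% of patients having a gap: if 2% or 5% do, a 10% rate becomes 9.8% or 9.5%. All of this stands, and it limits the size. It does not justify a score below the worst possible outcome.

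Three stronger readings are tempting, and the documents do not support them.

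- *That the rule contradicts the 50% and 75% rule.* These are separately stated rules for different endpoints. Using available months here would score (1, 1, missing) as 1.00, above an observed failure, which would be generous for a complete-response endpoint. The month-level fix does not follow the 50%/75% rule either.
- *That the treatment comparison is biased as it stands.* With missingness equal between arms and unrelated to response, the ratio is unchanged. Distortion of the kind calculated here needs missingness that differs by arm, and the documents give no evidence of that.
- *That averaging is itself an error.* It is prespecified with a worked example and matched by the choice of test. Panel 1 of the SAP names a 100% reduction in monthly migraine days over Weeks 1-12 and does not say that every month must qualify. What remains is a labelling point.

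**Conclusion.** The missing-month sentence is wrong as written. Under its literal terms a missing month scores below a failed one for any patient with an observed 100%-response month: 0 against 0.67 over 12 weeks, and 0 against 0.83 over 24 weeks. That follows from the text alone.

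The effect on results depends on assumptions. At a 10% true rate in both arms and 3% versus 8% of months missing independently of each other and of response, the rule creates a difference of about 1.3 points where month-level non-response creates 0.5. The excess shrinks as missing months cluster. With equal missingness the rule lowers the rates but leaves the ratio between arms unchanged.

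The affected endpoints are 100% response in MMDs and MHDs: secondary for Weeks 1-12, exploratory in the long-term part. They lie outside the testing strategy in SAP 12.2 and carry nominal p-values, so no primary or key secondary conclusion is touched. The point should be corrected, but it does not threaten the trial's main claims.

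**What to change.** In SAP 19.1.1.2, replace the last sentence so that only the missing month's status is set to 0 before the months are averaged. Apply this to MMDs and MHDs and to 12- and 24-week intervals. If the sponsor always meant the zero for the month alone, the same edit is needed, because a programmer following the present sentence would code something else.

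Label the result *average monthly 100% responder rate*. The proportion of patients with 100% response in every month, counting a missing month as failure, can be shown beside it as an optional descriptive row.

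The cost is one sentence, a table label and at most one extra row, with no new data. Timing matters: the summary of changes in protocol edition 3.0 describes sponsor personnel as unblinded after the database lock for the Placebo-controlled Period. If those data are already unblinded, keep the prespecified derivation and report the corrected one beside it as a supplementary analysis.
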